Part B (Cohorts B1 through B8): As guided by the BOP2 design, up to 40 patients per cohort will be enrolled initially into Cohorts B1-B4 and B6-B8. In Cohorts B1-B4 and B6-B8, patients will be treated with 800mg NM21-1480 to be administered approximately every 14 days. For Cohort B5, initial patients randomized to the NM21-1480/PD1 checkpoint inhibitor (pembrolizumab) arm will be administered the 800mg flat dose of NM21-1480 approximately every 14 days. There will be an enrolment stop after 6 patients have been enrolled to the NM21-1480/anti-PD1 combination arm. Only upon safety data review and clearance of this NM21-1480 dose level as a tolerable dose in the combination therapy setting by the SMC, the remaining patients are to be enrolled to Cohort B5. Once an MTD has been determined for NM21-1480 in this Cohort B5 combination setting, remaining patients may only be assigned to NM21-1480 dose levels at or below this combination therapy MTD for NM21-1480.

For the primary goal of assessing clinical response in Part B, depending on recruitment and availability of primary efficacy data, an interim futility analysis will be conducted for each cohort after 25 patients have response data following completion of 2 assessment cycles (i.e., 12 weeks). No such interim analysis will be done for Cohort B5 though. Dose groups may be pooled within cohorts for analysis if the response is deemed independent of dose from a PD/clinical perspective.

For Cohort B5, a total of approximately 200 patients with head and neck squamous cell cancer may ultimately be randomized 2:1 to either NM21-1480 plus a PD-1 standard-of-care first-line checkpoint inhibitor or to the standard-of-care PD-1 checkpoint inhibitor monotherapy. Randomization will be stratified by combined positive score (CPS ≥ 1 ; CPS ≥ 20), as determined by an FDA-cleared or any PD-L1 test approved for use by local competent authority. An interim analysis will be performed after 60 patients (40 patients in the NM21-1480 arm) have been enrolled. At this point, recruitment will be paused, the accumulated data analysed and regulatory authorities consulted. As with the other cohorts, decisions at this interim point will be taken based on clinical and regulatory input and not formal statistical testing.

Key Inclusion Criteria:

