 - dd. For Cohort B2 and Cohort B5 only: Pre-screening visit only required if HPV positivity has not previously been determined for the current tumor (or if criteria described in footnote ee are met). In case HPV positivity has previously been confirmed, no new HPV testing is required for eligibility. If HPV status is unknown, HPV positivity must be confirmed for eligibility by local testing, applying the standard local testing approach for the given tumor, while use of the CINtec p16 histology assay, another p16 immunohistochemistry assay, or a locally established RT-PCR or PCR test is recommended.
 - ee. For Cohort B2, Cohort B5, and Cohort B8 only: Pre-screening visit only required if PD-L1 expression status has not previously been determined for the current tumor (or if criteria described in footnote dd are met). In case PD-L1 expression in at least 1% of tumor and/or immune cells has previously been confirmed, no new PD-L1 testing is required for eligibility. If PD-L1 expression status is unknown, PD-L1 expression in at least 1% of tumor and/or immune cells must be confirmed for eligibility by local testing, using any PD-L1 test approved or cleared for use by the local competent authority.
 - ff. Sites are requested to attempt gathering and submitting the last pre-baseline scans for a patient as part of the tumor-specific therapy history; unavailability of these pre-baseline scans do not, however, make a patient ineligible for the study.
 - gg. Mandatory fresh, paired biopsy to be taken during screening period and at Day 21±3. **This only applies to patients with mCRC enrolled to Cohort B8.** The on-treatment biopsy can be delayed to the next clinically feasible day closest to Day 21 in situations in which as per investigator judgement taking the biopsy is not clinically feasible at the scheduled day. In any case, on-treatment biopsies should not be taken at days of dosing with NM21-1480. Both baseline as well as matched on-treatment biopsies. Fresh biopsies can be taken from primary tumor or metastases. At least 3 biopsy cores, but preferably more if considered safe by the radiologist, shall be taken at each biopsy event and touch preparation as per site standard approach shall be applied to ensure specimen adequacy (i.e., confirm tumor content). Further details are described in the laboratory manual. In addition to these

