 - bb. For Cohort B3 only: The screening process is to be conducted in 2 subsequent steps. Following signature of the ICF, PD-L1 expression scoring on tumor cells needs to be conducted either based on archival or fresh biopsy material from the TME and conducted centrally using a Sponsor-approved PD-L1 assay prior to entering the formal 28-day screening period. Only upon determination of a PD-L1 tumor cell expression score qualifying for study inclusion, the remaining eligibility criteria will be assessed.
 - cc. For Cohort B2 and Cohort B5 only: Pre-screening visit only required if HPV positivity has not previously been determined for the current tumor (or if criteria described in footnote dd are met). In case HPV positivity has previously been confirmed, no new HPV testing is required for eligibility. If HPV status is unknown, HPV positivity must be confirmed for eligibility by local testing, applying the standard local testing approach for the given tumor, while use of the CINtec p16 histology assay, another p16 immunohistochemistry assay, or a locally established RT-PCR or PCR test is recommended.
 - dd. For Cohort B2, Cohort B5, and Cohort B8 only: Pre-screening visit only required if PD-L1 expression status has not previously been determined for the current tumor (or if criteria described in footnote cc are met). In case PD-L1 expression in at least 1% of tumor and/or immune cells has previously been confirmed, no new PD-L1 testing is required for eligibility. If PD-L1 expression status is unknown, PD-L1 expression in at least 1% of tumor and/or immune cells must be confirmed for eligibility by local testing, using any PD-L1 test approved or cleared for use by the local competent authority.
 - ee. Sites are requested to attempt gathering and submitting the last pre-baseline scans for a patient as part of the tumor-specific therapy history; unavailability of these pre-baseline scans do not, however, make a patient ineligible for the study.

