- Cohort B4 will be conducted in the US, Spain, UK, the Netherlands, Germany, Taiwan, Turkey, Georgia, and Ukraine. For Cohort B4, patients must have a history of primary platinum-based chemotherapy with a maximum of 3 prior cytotoxic regimens and with at least one regimen for recurrent disease containing a platinum or a taxane for those with 3 prior regimens; the last platinum-free interval must be \leq 12 months. Histologic confirmation of the original primary tumor is required via the pathology report. NOTE: Patients with mucinous or carcinosarcoma history are not eligible.
- Patients are allowed to have received up to 3 prior cytotoxic regimens for treatment of their epithelial ovarian, fallopian tube, or primary peritoneal cancer;
 - they must have had one prior platinum-based chemotherapeutic regimen for management of primary disease, which could include intra-peritoneal therapy, consolidation, biological/targeted (non-cytotoxic) agents or extended therapy (maintenance/consolidation) administered after surgical or non-surgical assessment;
 - patients are allowed to have received, but are not required to have received, one to 2 cytotoxic regimens for management of recurrent or persistent disease;
 - PARP inhibitors given for recurrent or progressive disease will be considered cytotoxic;
 - PARP inhibitors given as maintenance therapy in continuation with management of primary disease will not be considered as separate cytotoxic regimen;
 - if 2 cytotoxic regimens had been received for management of recurrent or persistent disease, one of these regimens would have had to contain either a platinum or a taxane agent

- Platinum-free interval (PFI) – patients must have progressed ≤ 12 months after completion of their last platinum-based chemotherapy; the date (PFI) should be calculated from the last administered dose of platinum therapy to documentation of progression
- Cohort B5:
 - Patients with head and neck squamous cell cancer with documented CPS ≥ 1 in the TME and as determined by an FDA-cleared* or any PD-L1 test approved for use by competent authority

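### The schedule-of-assessments footnotes make HPV positivity an entry condition for Cohort B5, but the B5 eligibility criteria contain no HPV requirement

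*Protocol*

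**What the plan says.** Protocol Section 7.1.6, Table 7-1, footnote dd reads: "For Cohort B2 and Cohort B5 only: Pre-screening visit only required if HPV positivity has not previously been determined for the current tumor". It then says that a tumour already known to be HPV-positive needs no repeat test and that, where status is unknown, "HPV positivity must be confirmed for eligibility by local testing". Footnote cc to Table 7-2, the backup schedule for three-week dosing, carries the same rule: "If HPV status is unknown, HPV positivity must be confirmed for eligibility by local testing". A note under each table says that screening assessments decide eligibility.

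The companion PD-L1 footnote (ee in Table 7-1, dd in Table 7-2) covers three cohorts: "For Cohort B2, Cohort B5, and Cohort B8 only: Pre-screening visit only required if PD-L1 expression status has not previously been determined". It continues: "In case PD-L1 expression in at least 1% of tumor and/or immune cells has previously been confirmed, no new PD-L1 testing is required for eligibility". Where PD-L1 status is unknown, a local test must show the same percentage.

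Section 7.2.1 defines B5 in other terms: "Patients with head and neck squamous cell cancer with documented CPS" of at least 1, with incurable recurrent or metastatic disease, in patients who would receive an approved anti-PD-1 agent alone as labelled first-line treatment. The only B5-specific exclusion in Section 7.2.2 is earlier checkpoint-inhibitor treatment. On allocation the Synopsis says: "Randomization will be stratified by combined positive score". Section 10.5 sets the strata at CPS 1 to below 20 and CPS 20 or above.

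**The concern.** The protocol gives two entry rules for its only randomised cohort, planned at about 200 patients, and they disagree about HPV. HPV-positive disease defines Cohort B2; nothing in the B5 rationale, criteria, strata or model presents it as part of B5. Section 7.2 forbids eligibility waivers, so a site cannot settle the conflict case by case.

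What is at stake is which population B5 studies. HPV screening comes before randomisation, so applying either rule would not in itself bias the comparison between arms. It would decide whom the result describes, and mixed practice across sites would leave that population undefined.

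The PD-L1 footnote raises a smaller issue of the same kind. It tells a site that PD-L1 testing is complete on a measure that is not the one B5 uses for eligibility or stratification.

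**Working it through.** The claim rests on no sample size, error rate or effect size, so there is no planned figure to reproduce. The check is a comparison of texts.

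**HPV in each place that defines B5 (protocol)**

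| Place | HPV requirement for B5 |
|---|---|
| Synopsis, cohort description and key criteria | none |
| Section 7.1, cohort description | none |
| Section 7.2.1, inclusion | none (B2 has one) |
| Section 7.2.2, exclusion | none |
| Section 10.5, stratification | none; CPS only |
| Section 10.6.2.1, primary model | none; treatment and CPS terms only |
| Table 7-1 footnote dd | positivity must be confirmed if status is unknown |
| Table 7-2 footnote cc | same |

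No text reconciles the last two rows with the others.

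**A patient who meets every B5 criterion in Sections 7.2.1 and 7.2.2**

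1. HPV-positive on record: accepted under both rules.
2. Status unknown, test positive: accepted under both.
3. Status unknown, test negative: accepted by Section 7.2.1, not eligible under the footnote.
4. Status unknown, not tested: accepted by Section 7.2.1, not eligible under the footnote.
5. HPV-negative on record: accepted by Section 7.2.1; the footnote does not say what happens.

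Cases 3 and 4 contradict each other outright. Case 5 is left open.

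**PD-L1, for a patient whose record shows only that 1% or more of cells are positive**

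1. Under the PD-L1 footnote, no further test is needed.
2. Section 7.2.1 requires all inclusion criteria, among them a documented CPS of at least 1. The documents give no conversion from percentage of cells to CPS, so this is not yet shown.
3. Section 10.5 needs the CPS category, which the percentage does not supply.
4. The patient therefore cannot be randomised until a CPS exists, yet the footnote does not send the site to obtain one.

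**Size.** The number of patients affected depends on the HPV-positive share among otherwise eligible B5 patients and on how many arrive with unknown status. The documents give neither. The planned screen-failure rate does not help: Section 7.1.2 assigns 25% to B2, which requires HPV positivity, and the same 25% to B5.

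**The case against.** The best defence is that Sections 7.2.1 and 7.2.2 are the operative eligibility lists and that the footnotes only govern when a pre-screening visit and a test are needed. On that reading, no HPV ground exists for refusing a B5 patient. In addition, Table 7-2 applies only if the dosing interval is lengthened, and SAP Section 6 reports that nobody was enrolled in B5.

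For PD-L1 this defence largely succeeds: the inclusion criteria still demand a CPS, and the footnote does not displace them. Section 5.2 also describes the first-line head and neck setting by the percentage measure, so the protocol uses the two loosely. For HPV it does not succeed. The footnote ties a positive result expressly to eligibility, the table note gives screening assessments that function, and a site cannot both require and not require the same finding. Lack of enrolment limits the consequence but does not remove the contradiction.

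A reader might infer more than the documents support:

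- **Every HPV-negative patient would be excluded, and the result would apply to HPV-positive disease only.** The mandatory sentence covers unknown status, documented negatives are not addressed, and compliance across sites could have been mixed.
- **Screening would need to rise two- to fivefold.** This is 1/0.5 = 2 and 1/0.2 = 5 for assumed HPV-positive shares of 50% and 20%. The shares are not in the documents, so the result only restates the assumption.
- **The control-rate prior would be wrong.** Section 10.6.2.1 centres it near 20% from a pembrolizumab study. The protocol gives neither that study's HPV mix nor response by HPV status, so no mismatch can be shown.
- **The CPS covariate would be missing for some patients.** A patient without a CPS fails Section 7.2.1 and cannot be assigned to a stratum, so would not be randomised or reach the model.

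**Conclusion.** The HPV contradiction is real. Table 7-1 footnote dd and Table 7-2 footnote cc state an eligibility condition for B5 that the B5 criteria do not contain, and following the schedule would turn away patients whom Section 7.2.1 accepts. This conclusion needs no assumption beyond reading the footnotes as written.

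The PD-L1 wording is secondary. For B5 it names a result that neither establishes CPS eligibility nor assigns the stratum, but the inclusion criteria and the stratified randomisation still require CPS.

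The shift in population cannot be quantified from the documents. The practical consequence is limited: SAP Section 6 reports no B5 patients and SAP Section 4 refers to early closure of the trial. This is an internal inconsistency to correct in the protocol text, with no effect on any planned or reported analysis of enrolled patients.

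**What to change.** Reconcile the four footnotes with Section 7.2.1.

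- **HPV (Table 7-1 footnote dd, Table 7-2 footnote cc).** All other B5 text supports deleting Cohort B5, leaving these footnotes to B2. If the sponsor did intend HPV selection, then the Synopsis, Section 7.2.1, the screening estimate in Section 7.1.2 and the B5 design assumptions in Section 10.6.2.1 must state and justify it.
- **PD-L1 (Table 7-1 footnote ee, Table 7-2 footnote dd).** Give B5 its own sentence: a documented CPS of at least 1, with the category (1 to below 20, or 20 and above) recorded before randomisation, and CPS scoring where only a percentage-of-cells result exists.

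The cost is a text amendment to four footnotes. Some patients would need CPS scored, using tumour tissue that Section 7.2.1 already requires at screening. With no B5 enrolment there is nothing to re-analyse; the correction matters if B5 is opened or its text is reused in another protocol.
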